5 STUDY DESIGN

5.1 Study description

This is a Phase 2, open-label, multicenter study in children and adolescents with moderately to severely active CD who completed C87035, or were terminated from C87035 when the study was stopped by UCB, to assess the longterm safety and tolerability of CZP.

All subjects who complete Week 62 of C87035 or were terminated from C87035 when the study was stopped by UCB (and completed all assessments required for Week 62/Visit 23 at the time of termination) are eligible for entry.

Subjects may continue on CZP at the dose they were receiving at the end of C87035 (Low-Dose Group or High-Dose Group [weight adjusted in kg; see [Section 7.2](#) and [Table 7-1](#)]) every 4 weeks until the subject reaches the age of 18 years or CZP is approved for use in the US by pediatric subjects with CD. The first clinic visit should coincide with the last visit of C87035 (Week 62/Visit 23). First study drug administration occurs 2 weeks later (Week 2) and subsequent clinic visits for safety and efficacy assessments are scheduled at 12-week intervals. After Week 2, subjects or parents/caregivers/appropriate designee as determined by the Investigator have the option of home administration of CZP upon appropriate training during a previous clinic visit(s) or continuing to have CZP administered every 4 weeks at the clinic. For subjects performing home administration, a phone call to the subject and/or the parents/caregiver will be performed by the Investigator (or designee) every 4 weeks between regular clinic visits in order to capture potential AEs and changes in concomitant medications, and to check compliance with home dosing. An SFU Visit will be conducted 12 weeks after the last dose of study medication for subjects.

Please refer to Study Schedule of Assessments in [Section 5.2](#) for visit-specific procedures and to [Section 5.3](#) for a schematic representation of the study.

A DSMB will periodically review all emerging safety data (see [Section 13.8](#)). Based on the safety data, the DSMB can recommend modifying or stopping the study.

Loss of response/reinduction

- *Subjects who were reinduced in C87035 are not eligible for reinduction in CR0012. Should loss of response occur in CR0012, the subject must be withdrawn.*
- *If there was no reinduction in C87035, 1 reinduction only is permitted in CR0012. If response is lost a second time in CR0012, the subject must be withdrawn.*

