Loss of response, defined as an increase in PCDAI ≥ 15 points compared to Week 6 of C87035 at 2 consecutive visits at least 1 week apart, or an overall PCDAI > 30 points at any time, will result in reinduction and dosing as follows:

- The reinduction dose will be adjusted to the subject's weight: 400mg for subjects ≥ 40 kg or 200mg for subjects 20 to < 40 kg sc Q2W for a total of 3 doses
- Continue dosing with CZP administered sc Q4W as 400mg for subjects ≥ 40 kg or 200mg for subjects 20 to < 40 kg, regardless of the subject's previous randomized dose group

Summary of visits related to loss of response

1. Loss of response must be confirmed at a clinic visit where assessments and labs are performed to determine PCDAI score. Scores cannot be confirmed until lab results are received by central lab a few days after the clinic visit. Once loss of response is confirmed, sites must contact the subject to return for the first Reinduction Visit.
2. Reinduction Week 0 - subjects will receive the first dose for reinduction at the clinic.
3. Reinduction Week 2 occurs 2 weeks later for second dose at the clinic.
4. Reinduction Week 4 occurs 2 weeks later for third dose at the clinic.
5. Subject resumes the original schedule of clinic visits after reinduction. The clinic should contact the Study Monitor to determine the most appropriate way to resume the original schedule of clinic visits.

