^bAfter Week 2, subjects or parents/caregivers have the option of home administration of CZP upon appropriate training during a previous clinic visit(s) or can continue to have CZP administered every 4 weeks at the clinic. For subjects performing home administration, a phone call to the subject and/or the parents/caregiver will be performed by the Investigator (or designee) every 4 weeks between regular clinic visits in order to capture potential AEs and changes in concomitant medications, and to check compliance with home dosing. Subjects will have the option to either switch to home dosing or switch

Table 5-1. Schedule of study assessments

Visit or phone call (+/-7 days)	Treatment Period						
	Entry ^a	Visit	Phone call (home administration) or visit (clinic administration) ^b	Regular Clinic Visits ^b	Completion/Early Termination	Unscheduled Visit ^c	SFU ^d
Week	0	2	Every 4 weeks beginning at Week 6 and in between regular clinic visits	Every 12 weeks beginning at Week 14			+12 weeks after last dose of study drug

back to site administration at anytime during the study.

^cVital signs, concomitant medication, and AEs must be assessed at every Unscheduled Visit. Other safety and PK assessments (eg, CZP plasma sample) may be performed at the discretion of the Investigator as related to the nature of the visit.

^dThe SFU Visit should be performed 12 weeks after the final dose of study medication. For subjects continuing directly onto commercial CZP, a SFU Visit should be completed prior to the first dose of commercial drug administration.

^eFor all females post menses, a urine pregnancy test will be conducted at all regularly scheduled clinic visits except Week 2.

^fVital signs will be collected 15 minutes prior to dosing with a ± 5 minute window.

^gDays missed from school will be assessed using the WPAI:CD for children. The time missed from work will be assessed using the WPAI:CD for working individuals with CD. The effect of the child's CD on the caregiver's productivity will be assessed using the WPAI:CD for caregivers of children with CD.

^hPlasma samples will be collected to determine the concentration of CZP every 12 weeks starting at Week 14, and at the Completion/Early Termination and SFU Visits. Samples will be collected before dosing (except for the Completion/ET and SFU Visits when there is no dosing).

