Investigators should attempt to obtain information on subjects, in the case of withdrawal or discontinuation. For subjects considered as lost to follow-up the Investigator should make an effort (at least 1 phone call and 1 written message to the subject), and document his/her effort (date and summary of the phone call and copy of the written message in the source documents) to complete the final evaluation. All results of these evaluations and observations, together with a narrative description of the reason(s) for removing the subject, must be recorded in the source documents. The case report form (CRF) must document the primary reason for withdrawal or discontinuation.

Investigators should contact the Medical Monitor whenever possible to discuss the withdrawal of a subject in advance.

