8 STUDY PROCEDURES BY VISIT

During the study, the acceptable window between the study visits is +/-7 days relative to entry (Week 0).

8.1 Entry Week 0

Week 0 of CR0012 is equivalent to Week 62 of C87035 with the exceptions noted below. Subjects who were terminated from C87035 when the study was stopped by UCB completed all assessments required for Week 62/Visit 23 at the time of termination.

Before any study-related procedures are performed, an IRB/IEC approved informed consent will be properly executed and documented. The written informed consent of the child's parent(s)/legally acceptable representative(s) must be obtained. In addition, where requested by local laws or by the IRB/IEC and according to the child's age/competence, the Assent form should be obtained from the child. The subjects and their parent(s)/legally acceptable representative(s) will be given adequate time to consider any information concerning the study given to them by the Investigator or designee. As part of the informed consent procedure, subjects and their parent(s)/legally acceptable representative(s) will be given the opportunity to ask the Investigator any questions regarding potential risks and benefits of participation in the study.

Assessments to be performed include:

- Written informed consent
- Inclusion/ exclusion criteria
- Demography
- TB test
- TB questionnaire

The following ongoing information must be continued to be followed from C87035 to CR0012:

- Adverse events
- Concomitant medications

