3.5 Analysis sets

The All Subject Population will include those subjects who are enrolled in the study. All available data entered into the database will be listed for this population.

The Safety Population will include all subjects enrolled who receive at least 1 injection of study treatment in this study. This population will be used to summarize the safety, PK, and immunological variables.

The Intention-to-Treat (ITT) Population will include all subjects irrespective of any protocol deviations who receive at least 1 injection of study treatment in this study and who have at least 1 efficacy measurement after the first injection of this study. This population will be used to summarize the efficacy variables.

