7 MEASUREMENTS OF TREATMENT COMPLIANCE

The number of weeks completed, number of expected doses, and number of doses received will be listed for the Safety Population. Definitions are provided below:

- Total weeks completed = $[(\text{last dose date} - \text{first dose date} + 1) / 7]$
 - If total weeks completed is <2 , then total expected doses = 0 since first study dose administration begins at the Week 2
- If the subject did not re-induce, then
 - total expected doses = $(\text{total \#weeks completed} / 4) + 1$ rounded down to the nearest integer
- If the subject did re-induce, then
 - total expected doses = $(\text{total \#weeks} / 4) + 2$ rounded down to the nearest integer

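### SAP 7 expects no dose from a one-dose subject, and one dose too few when the dosing span is 2 to 14 days short of nominal

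*SAP*

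**What the plan says.** SAP 7 (Measurements of treatment compliance) lists weeks completed, expected doses and doses received for the Safety Population. Weeks completed is the last dose date minus the first dose date, plus 1, divided by 7. If that is below 2, "then total expected doses = 0 since first study dose administration begins at the Week 2". Otherwise expected doses are weeks divided by 4, plus 1 (plus 2 if the subject was re-induced), "rounded down to the nearest integer".

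Three other places bear on this:

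- SAP 3.5 defines the Safety Population as "all subjects enrolled who receive at least 1 injection of study treatment in this study", so every listed subject has received at least one dose.
- Protocol 5.1 places the first dose after entry: "First study drug administration occurs 2 weeks later (Week 2". Dosing is then every 4 weeks.
- Protocol 8 states that "the acceptable window between the study visits is +/-7 days relative to entry (Week 0", and the header of Table 5-1 gives the same 7 days for visits and phone calls.

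**The concern.** The reason given for the zero rule fits a clock that starts at entry, but the SAP's clock starts at the first dose. The 2-week lead-in is therefore taken off twice, and the rule can produce an expected count below the minimum that membership of the listed population guarantees.

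Rounding down is a separate problem. The formula tolerates only the one early day supplied by its own plus 1, while the protocol lets the first dose be up to 7 days late and the last up to 7 days early.

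What is at stake is how the listing reads. Received above expected looks like an extra or misrecorded dose in a subject who followed the schedule. An expected count that is one too low can also cancel a genuine missed dose.

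**Working it through.** **Inputs.** D = last dose date minus first dose date, in days; W = (D + 1)/7 (SAP 7). The dosing interval is 28 days (SAP 3.2). The visit window is +/-7 days around nominal days fixed from Week 0 (Protocol 8). I take that window to apply to the doses due at those visits or calls.

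**Formula.** For a subject not re-induced, expected = 0 if W < 2; otherwise floor(W/4 + 1) = floor((D + 1)/28) + 1.

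**One dose.** D = 0, so W = 1/7 = 0.14, which is below 2. This reproduces the SAP's stated 0. The general formula alone gives floor(1/28) + 1 = 1, which matches the one dose received.

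**Who else meets the zero rule.** W < 2 needs D of 12 days or less. The closest two scheduled doses within the window are Week 2 given 7 days late (day 21) and Week 6 given 7 days early (day 35): D = 14, W = 15/7 = 2.14. No subject with two in-window 4-weekly doses is caught. A re-induction dose within 12 days of the first dose would be, and 0 would then be further from the truth.

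**Rounding.** A fully dosed subject with k intervals has k + 1 doses, and D can lie from 14 days under to 14 days over 28k. For 13 doses (k = 12, nominal D = 336):

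| D | Offset | (D + 1)/28 | SAP expected | Scheduled |
|---|---|---|---|---|
| 350 | +14 | 12.54 | 13 | 13 |
| 336 | 0 | 12.04 | 13 | 13 |
| 335 | -1 | 12.00 | 13 | 13 |
| 334 | -2 | 11.96 | 12 | 13 |
| 322 | -14 | 11.54 | 12 | 13 |

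For k from 1 to 59, offsets of -2 to -14 days are always exactly one dose short, and offsets of -1 to +14 are right. If weeks were first rounded to the nearest integer, which the SAP does not say, the shortfall would run from -5 to -14: D = 332 gives 13 and D = 331 gives 12.

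**Hidden miss.** Thirteen doses scheduled, D = 334, one missed mid-course: 12 expected, 12 received.

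**Re-induced subjects.** Re-induction gives three doses two weeks apart, one more than the 4-weekly schedule over the same four weeks. If it starts on a scheduled dosing day and is completed, D = 336 gives floor(337/28) + 2 = 14, which is right. D = 334 gives 13, the same one-dose shortfall. If the subject stops after the first re-induction dose on scheduled day 28k, k + 1 doses fell due but the formula gives k + 2, one too many.

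**The case against.** The best defence is that this is one descriptive listing for 16 subjects (SAP 4.4). It prints weeks completed beside both dose counts, so a reader can see a near-zero span or recompute. Nothing in SAP 8.1 says that exposure uses expected doses, and no compliance percentage or analysis set is built on them. Missed doses have other routes: reporting to the Medical Monitor (Protocol 7.7) and the treatment non-compliance category of deviations (SAP 5.2). All of this stands and limits the severity. It does not make the listed values right.

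Several stronger readings are tempting but not supported:

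- A reader might infer that any span 2 or more days under a multiple of 28 is miscounted. The error stops at 14 days. D = 64 is 20 days under 84, yet floor(65/28) + 1 = 3, which is correct for three doses with the last 8 days late.
- Of the 29 permitted whole-day offsets, 13 are undercounted (10 if weeks are rounded to the nearest integer). That is not a frequency. If first and last doses fell independently and uniformly over their windows, the share would be 91/225 = 40%, but the documents give no dose dates to support that assumption. Nor do they show that any subject had only one dose.
- A reader might call it an error that the clock ends at the last dose taken, so doses missed afterwards are never expected. That is the SAP's stated definition. It is a limitation of the listing rather than a slip in it.
- A reader might take the plus 2 as exact, or as always wrong. It is right in the case worked above. However, Protocol 5.1 does not tie re-induction to a scheduled dosing day: "Scores cannot be confirmed until lab results are received by central lab a few days after the clinic visit", and the subject is then called back.

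**Conclusion.** Both errors hold when the SAP is followed exactly. A one-dose subject is listed as 0 expected and 1 received. A fully dosed subject is one dose short on expected doses when the span is 2 to 14 days under nominal, and the re-induction branch has the same shortfall. The second result assumes that the +/-7-day window governs dosing days and that weeks are not rounded first; rounding them to the nearest integer moves the lower limit to 5 days.

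Severity is minor. The error in the rounding is always a single dose, in one by-subject listing, and no other analysis is shown to depend on it. The number of subjects affected cannot be determined from the documents and could be none.

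**What to change.** 1. Delete the line that sets expected doses to 0 when weeks completed is below 2.
2. For subjects not re-induced, replace rounding down with 1 + ROUND((last dose date - first dose date)/28). This is right for fully dosed subjects at every permitted offset except exactly +14 days, where it gives one too many. Alternatively, use 1 + ROUND((last dose date - Week 0 date - 14)/28). A last dose within +/-7 days then moves the quotient by at most 7/28 = 0.25, so the count is right throughout the window.
3. For re-induced subjects, count the re-induction and 4-weekly doses that fell due up to the last dose date, instead of adding a fixed 2.

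The cost is a few lines of SAP text and one derivation, using dose dates and, for the alternative, the Week 0 date. Doses missed after the last dose taken are still not counted. Counting them would need a treatment-stop date separate from the last dose date, and the documents do not say that one is collected; Protocol 6.3 says only that the CRF "must document the primary reason for withdrawal or discontinuation".

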8 SAFETY ANALYSES

All safety summaries will be based on the Safety Population and presented by dose group (separate columns for High Dose and Low Dose), and presented by weight category, and by age category, as appropriate.

For all by-visit AE and medication summaries, if a subject in the Low Dose group is re-induced, the subject will be summarized under the High Dose column from the time of re-induction onwards.

8.1 Extent of exposure

Descriptive statistics for the duration of CZP exposure (in years), and for CZP exposure (in mg) during the study will be presented by dose group and Total.

8.2 Adverse events

Treatment-emergent adverse events (TEAEs) will be summarized descriptively by primary SOC and PT. Table columns will include dose groups of CZP Low Dose, CZP High Dose, CZP Re-induction 400mg, and All CZP Doses, and report incidence, percent, and number of TEAEs. AEs will be defined as related to treatment if the relationship is recorded as possible, probable, highly probable, or missing. AEs will be defined as not related if the relationship is recorded as unlikely or none.

An overall summary of TEAEs, including the number of events, the number and percentage of subjects with any TEAE, with each severity, with each relationship to treatment, treatment related (defined as possible, probable, highly probable, or missing), SAEs, any TEAEs leading to withdrawal from the study, any TEAEs requiring dose change, and any TEAEs leading to death will be presented by dose group.

Other treatment-emergent adverse event tables will include:

- All TEAEs by primary SOC and PT
- All TEAEs by primary SOC, PT, and severity
- All TEAEs by primary SOC, PT, and relationship to study drug

- All TEAEs sorted by incidence in the All CZP Doses group by PT
- SAEs by primary SOC and PT
- Non-serious TEAEs with an incidence of >5% in the All CZP Doses group by primary SOC and PT
- TEAEs leading to withdrawal from the study by primary SOC and PT
- TEAEs occurring within 30 minutes of receiving an injection by primary SOC and PT
- Injection site reactions by primary SOC and PT
- Systemic injection reactions by primary SOC and PT
- SAEs by primary SOC, PT, and relationship
- Non-serious TEAEs by primary SOC, PT, and relationship
- TEAEs leading to death by primary SOC, PT, and relationship
- Non-serious TEAEs with an incidence of >5% in the All CZP Doses group by primary SOC, PT, and relationship
- Adverse Events of interest

Adverse events (AEs will be coded using the Medical Dictionary for Regulatory Activities (MedDRA), Version 20.1. AEs of interest and the approach to summarize them will be briefly described below. Further information is provided in the guidance document (AE's of Interest – Cimzia Program 5 January 2018).

1. Serious infections, including opportunistic infections will be manually identified by a study physician using the Serious TEAE table. A separate table does not need to be produced. Opportunistic infections (including tuberculosis) will be summarized in a stand-alone table using UCB-defined search criteria.
2. Malignancies, including lymphoma will be presented in 2 tables using the Standardized MedDRA Query (SMQ) criteria “Malignant or unspecified tumours” and “Malignant tumours” respectively.
3. Serious cardiovascular events will be presented in a table using the following search criteria
 - a. Serious cardiovascular events will be presented in a table using the following search criteria
 - i. Serious cardiovascular events will be presented in a table using the following search criteria:
 1. Conditions associated with central nervous system haemorrhages and cerebrovascular accidents (SMQ)
 2. Haemorrhagic central nervous system vascular conditions (SMQ)
 3. Ischaemic central nervous system vascular conditions (SMQ)
 - b. All serious TEAEs which code to a PT included in the HLT “Ischaemic coronary artery disorders” except events coding to PT “Chest Pain” or “Chest discomfort”
 - c. All serious TEAEs which code to a PT included in any of the following HLTs: “Heart Failures NEC”, “Left Ventricular Failures”, or “Right Ventricular

Failures” and which also code to the SOC of “Cardiac Disorders” as Primary SOC

4. Congestive heart failure AEs (defined as all AEs which code to a PT of “Cardiac failure congestive”) will be manually identified by the study physician using the “Any TEAE” table. A separate table does not need to be produced to summarize this event.
5. Demyelinating-like disorders will be presented in a stand-alone table which is based on the SMQ = “Demyelination”. The SMQ search should include all TEAEs which code to a PT included in Scope=Narrow group within the SMQ. TEAEs which code to a PT included in the Scope=Broad group within the SMQ should be excluded from the search.
6. Aplastic anemia, pancytopenia, thrombocytopenia, neutropenia and leucopenia will be presented in a stand alone tables based on the SMQ = “Haematopoietic cytopenias”. The SMQ search should include all serious TEAEs which code to a PT included in the Scope=Broad and/or Scope=Narrow groups within the SMQ.
7. Serious bleeding events will be presented in a stand-alone table that is based on the SMQ = “Haemorrhage terms (excl laboratory terms) (SMQ)”. The SMQ search should include all serious TEAEs which code to a PT included in the SMQ.
8. Lupus and lupus-like illness will be manually identified by the study physician using the “Any TEAE” table. A separate table does not need to be produced to summarize these types of events.
9. Serious skin reactions (eg, Stevens Johnson Syndrome, toxic epidermal necrosis, and erythema multiforme) will be manually identified by the study physician using the “Any SAE” table. A separate table does not need to be produced to summarize these types of events.

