9.3 Adverse events of interest

An AE of special interest is any AE which is listed in the European Risk Management Plan, or meets another commitment requiring nonstandard expedited reporting, even if the AE does

not fulfill the expedited reporting criteria of “serious”, “unexpected”, and “associated with the use of the drug.” Adverse events of special interest include:

- Serious infections including opportunistic infections
- Malignancies including lymphoma
- Congestive heart failure
- Demyelinating-like disorders
- Aplastic anemia, pancytopenia, thrombocytopenia, neutropenia, and leucopenia
- Serious bleeding events
- Lupus and lupus-like illness
- Serious skin reactions (eg, Stevens Johnson Syndrome, toxic epidermal necrosis, and erythema multiforme)

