13.3 Planned safety analyses

All safety summaries will be based on the Safety Population as a whole, by treatment group, weight, and age stratum.

Treatment emergent adverse events will be summarized descriptively by primary SOC, high level term, and PT. Additional tables will summarize AEs by severity and relationship to study drug, and separate tables will be generated for AEs leading to withdrawal from the study, SAEs, and deaths. Other AEs of special interest including, but not limited to, infections will also be summarized.

The specific set of AEs reported as injection reactions will also be summarized along with their classification as either injection site reactions or systemic hypersensitivity reactions (the latter being further classified as acute or delayed).

Actual laboratory values and changes from Baseline in laboratory values will be summarized. Shift tables to show the change from Baseline in the absolute values and details of treatment emergent markedly abnormal values (based on Common Terminology Criteria for Adverse Events criteria) will be presented by variable.

Actual vital signs values and change from Baseline in vital signs values will be summarized.

Autoantibody levels will be assessed via the presence or absence of ANA and anti-dsDNA, and data will be summarized.

Extent of exposure to treatment will be presented descriptively.

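### The SAP's adverse-event-of-interest table for cytopenias counts serious events only, although Protocol 9.3 sets no seriousness limit for that category

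*SAP*

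**What the plan says.** Protocol 9.3 lists eight categories of adverse events of interest. One of them is "Aplastic anemia, pancytopenia, thrombocytopenia, neutropenia, and leucopenia", with no qualifier. The same list does attach the word serious to infections, bleeding events and skin reactions. The definition that opens the section says that an event can be of special interest even if it does "not fulfill the expedited reporting criteria of “serious" and the other expedited-reporting conditions.

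Protocol 13.3 then plans the analysis: "Other AEs of special interest including, but not limited to, infections will also be summarized". It states no seriousness limit.

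SAP 8.2, item 6, repeats the protocol's five conditions without a qualifier and assigns them a stand-alone presentation based on the SMQ 'Haematopoietic cytopenias'. The search rule is: "The SMQ search should include all serious TEAEs which code to a PT included in the Scope=Broad and/or Scope=Narrow groups within the SMQ".

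The SAP handles the other four unqualified protocol categories as follows:

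- Item 2: "Malignancies, including lymphoma will be presented in 2 tables using the Standardized MedDRA Query (SMQ) criteria", with no seriousness limit stated.
- Item 4: "Congestive heart failure AEs (defined as all AEs which code to a PT of" cardiac failure congestive) are picked out by the study physician from the table of any TEAE.
- Item 5, demyelinating-like disorders: "The SMQ search should include all TEAEs which code to a PT included in Scope=Narrow group within the SMQ".
- Item 8: "Lupus and lupus-like illness will be manually identified by the study physician using the" table of any TEAE.

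**The concern.** The title of item 6 and its search rule describe different sets of events, and the rule is narrower than the protocol category. Someone who opens this table to learn how many subjects had a cytopenia would see serious cases only, and nothing in the title would say so. A zero could be read as no cytopenias when it means no serious cytopenias.

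Long-term safety and tolerability is the primary objective, and Protocol section 2 names pancytopenia among the infrequent serious events reported with TNF antagonists. What is at stake is whether one descriptive safety table shows the category it names. No test or estimate depends on it.

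**Working it through.** The documents give no cytopenia counts or rates and no planned figure to reproduce. The check is therefore a comparison of text, with one line of arithmetic.

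**Step 1. Protocol categories against SAP search rules.**

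| Protocol 9.3 category | Protocol says serious? | SAP 8.2 item | SAP limits to serious? |
|---|---|---|---|
| Infections | Yes | 1 | Yes, read from the serious TEAE table (opportunistic infections also get their own table, no limit stated) |
| Malignancies | No | 2 | None stated; two tables |
| Congestive heart failure | No | 4 | No; read from the any-TEAE table |
| Demyelinating-like disorders | No | 5 | No; stand-alone table, Narrow scope |
| Cytopenias | No | 6 | **Yes**; stand-alone table, Broad and/or Narrow scope |
| Bleeding events | Yes | 7 | Yes; stand-alone table |
| Lupus and similar illness | No | 8 | No; read from the any-TEAE table |
| Skin reactions | Yes | 9 | Yes; read from the SAE table |

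Three protocol categories carry the qualifier and five do not. Of those five, the SAP states a seriousness limit for one (item 6) and none for four (items 2, 4, 5 and 8). Three of the five have stand-alone tables (items 2, 5 and 6), and only item 6 is restricted. Item 7 uses nearly the same serious-only sentence as item 6, but there the label says serious as well, so label and rule agree.

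**Step 2. Where a non-serious cytopenia would still appear.**

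- In the all-TEAE tables and the table of non-serious TEAEs by relationship (SAP 8.2), as separate preferred-term rows.
- In subject listings (SAP 3.5).
- In the laboratory listings and the by-week laboratory summaries (SAP 8.3), which include the minimum (SAP 3.1).
- In the laboratory shift tables, which compare Baseline with end-of-trial status. A count that has recovered by then is not shown as low.
- In the markedly abnormal laboratory table, if Grade 3 or 4. The Grade 3 entry points in SAP 13.1 are neutrophils <1.0, white cells <2.0, platelets <50.0 and lymphocytes <0.5 (all x10E9/L), and hemoglobin <80 g/L. Each parameter is reported separately.

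Take a non-serious neutropenia AE whose lowest neutrophil count is 1.0 x10E9/L or above. It is in neither the Grade 3–4 neutrophil rows nor the item 6 table. It is in the general TEAE tables, as one preferred-term row.

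None of these outputs counts subjects with at least one cytopenia AE across preferred terms regardless of seriousness. Preferred-term rows cannot simply be added, because one subject may appear in several.

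**Step 3. Size per subject.** SAP 4.4 gives n = 16. If all 16 were dosed, each subject left out changes the all-doses percentage by 1/16 = 6.25 points. The change is larger within a dose-group column, but the documents do not give those column sizes.

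**The case against.** The best counter-argument is that Protocol 9.3 is a reporting rule. It defines these events by commitments to non-standard expedited reporting, and 9.4 uses the list for immediate reporting. Protocol 13.3 asks only for a summary, names no query or grouping, and section 13 leaves detail to the SAP. On that reading, the preferred-term tables already satisfy the protocol. It is true that the protocol does not prescribe the form of this table. But 9.3 is where the protocol defines the category that 13.3 promises to summarize, and the SAP's title adopts that category unqualified. A rule narrower than its own title is still an error.

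A second point is that SAP item 3c tabulates heart-failure terms for serious TEAEs only, so item 6 may not be alone. Item 3, however, is labelled as serious cardiovascular events, which is not a Protocol 9.3 category. Congestive heart failure itself is item 4 and is taken from all AEs.

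Third, item 6 may deliberately pair a wide query (Broad scope) with a seriousness filter, while item 5 pairs all TEAEs with Narrow scope. That is plausible, and searching all TEAEs with Broad scope kept could bring in terms beyond the five named conditions. But the SAP does not state this reasoning. It refers to a program guidance document of January 2018 that was not available for this review and may explain the rule.

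Fourth, coverage elsewhere is good: weekly laboratory minima show low values even above the Grade 3 cut, and 16 subjects can be reviewed by hand. This stands and limits the consequence. It does not supply the missing grouped count. Lupus and congestive heart failure also have no table of their own, but they have no table that appears complete and is not.

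**Conclusion.** The concern holds. As written, item 6 produces a table that omits any non-serious event in the category it names, and it disagrees with Protocol 9.3. The conclusion rests on current text in both documents and assumes that the unseen program guidance does not override the visible search rule.

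The number of omitted events cannot be derived and may be zero. The weight per subject is 6.25 percentage points of the all-doses column if all 16 subjects were dosed. No data are lost and no inference changes. This is a minor-to-moderate correction that should be made because the table serves the primary objective.

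**What to change.** In SAP 8.2, item 6, remove the seriousness limit so that the search takes all TEAEs in the SMQ 'Haematopoietic cytopenias', and show serious TEAEs as a subset row. If the serious-only convention is also kept, put the word serious in the title of that part and record it as a departure from Protocol 9.3 with the reason. Showing Narrow and Broad scope separately is optional, but it would keep the five named conditions distinguishable from wider terms.

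The cost is one word in the search rule and a few extra rows in one table. No new data are needed. The reported count may be less favourable and, if Broad scope is kept, may include terms outside the five conditions.
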